9.9.5. Ophthalmoscopy and Optical Coherence Tomography

A complete ophthalmoscopy and OCT will be performed according to the Schedule of Assessments ([Table 6](#)). OCTs occurring at the ET visit that are within 4 weeks of the last assessment (eg, Week 12) will only be required if clinically indicated. The 2-Week Follow-Up visit OCT assessment is only required if clinically indicated. A standard visual acuity chart should be used for the visual acuity assessment. The OCT machine used should preferably not be changed during the study to allow for comparison of central foveal thickness measurements within each participant across timepoints.

Screening visit:

At the screening ophthalmology visit, the eye examination will include:

- Ophthalmologic history
- Best corrected visual acuity measurement (using Landolt C chart)
- Ophthalmoscopy (may include contact lens biomicroscopy to examine the macula and optic disc). A dilated fundus exam should be performed in all participants at the

screening visit and as needed at subsequent visits in participants with significant abnormalities identified on the screening exam.

- Measurement of central foveal thickness by OCT (recorded in micrometers; required for all participants regardless of the results of visual acuity or ophthalmoscopy)
- Slit lamp examination should be performed to establish uveitis disease status (yes/no). Uveitis should be characterized and graded using the Standardization of Uveitis Nomenclature criteria. Participants with active uveitis without macular edema at Screening are eligible to enroll in the study
- If there is a suspicion of macular edema by ophthalmoscopy and increased central foveal thickness by OCT, then additional testing should be considered at the discretion of the ophthalmologist (for example, fluorescein angiogram may be performed). Participants with diagnosed macular edema at Screening should be deemed a screening failure and should not be randomized.
- Optional procedures in case of clinically significant abnormalities on ophthalmic exam may include but are not limited to:
 - Retinal photographs
 - Intraocular pressure

Scheduled post-screening visits:

At the scheduled ophthalmology visit, the eye examination will include

- Best corrected visual acuity measurement
- Ophthalmoscopy (may include contact lens biomicroscopy to examine the macula and optic disc)
- Measurement of central foveal thickness by OCT
- For participants with uveitis findings on ophthalmic exam, additional testing should be considered (for example, fluorescein angiogram)

Participants experiencing unexpected ophthalmic symptoms without a known suspected etiology or experiencing a relevant ophthalmic adverse event may need to have repeated ophthalmoscopy and OCT testing performed.

9.9.6. Tuberculosis Screening and Chest X-Ray

All participants will complete TB screening to determine eligibility. A TB screening questionnaire will be completed during the Screening Period by the Investigator or delegated site staff for each participant and applicable information will be entered into the eCRF. For participants who are receiving TB prophylaxis treatment, the TB questionnaire will be completed at every study visit (until TB prophylaxis treatment course is completed).

9.9.7. Clinical Laboratory Tests

Refer to [Table 5](#) for the list of clinical laboratory tests to be performed and the Schedule of Assessments ([Table 6](#)) for timing and frequency for each test. All scheduled clinical laboratory tests will be completed by a central lab or a sponsor approved regional lab for analysis unless extenuating

circumstances prevent shipments to a central lab (eg, natural disasters, war, etc.) in which case a qualified local laboratory can perform tests only once permission is granted by the Sponsor (or delegate). If a local laboratory is used for protocol-specified tests (even in parallel), this will be captured as a PD. Laboratory tests for a documented new or ongoing AE are not a PD. Details regarding clinical laboratory sample collection, preparation, and shipment are provided in the Laboratory Manual by the central laboratory.

Clinical safety laboratory tests should be completed predose. The Investigator must review the laboratory report, document this review, and record any clinically relevant changes occurring during the study in the adverse event section of the eCRF (results of the total WBC and ALC will be reviewed and monitored as described in Section 9.8.4). The laboratory reports must be filed with the source documents. Clinically significant abnormal laboratory findings are those that are not associated with the underlying disease, unless judged by the Investigator to be more severe than expected for the participant's condition.

All laboratory tests with values considered clinically significantly abnormal during participation in the study or within 30 days after the last dose of study treatment should be repeated until the values return to normal or baseline or are no longer considered clinically significant by the Investigator or Medical Monitor.

- If such values do not return to normal/baseline within a period of time judged reasonable by the Investigator, the etiology should be identified, and the Sponsor should be notified.
- All protocol-required laboratory assessments, as defined in the Schedules of Assessments (Table 6), must be conducted in accordance with the Laboratory Manual.
- If laboratory values from non-protocol -specified laboratory assessments performed at the institution's local laboratory require a change in participant management or are considered clinically significant by the Investigator (eg, adverse event, SAE, or dose modification), then the results must be recorded in the eCRF.

For guidance on monitoring participants with notable lymphopenia, please refer to Section 9.8.4.

See Section 16.6 for suggested actions and Follow-up assessments in the event of potential DILI.

Table 5: Clinical Laboratory Tests

SCREENING Only
Virology HIV, HBsAg, HBcAb , HBsAb, HBV DNA, HCV (RIBA)
Stool Sample Bacterial culture, ova and parasites, C. difficile
Drugs of Abuse Amphetamine, barbiturates, benzodiazepines, cocaine, methadone, methamphetamine, methylenedioxymethamphetamine, opiate, oxycodone, phencyclidine
Others Hemoglobin A1c, Interferon gamma releasing assay (IGRA) (eg, QuantiFERON or T-SPOT-TB)
PREGNANCY TESTING
Serum pregnancy test beta-human chorionic gonadotropin (β -hCG) - Screening Urine β -hCG (only for women of childbearing potential)

Table 5: Clinical Laboratory Tests (Continued)

CLINICAL CHEMISTRY, HEMATOLOGY, AND COAGULATION		
Hematology		Serum Chemistry
Hematocrit	Albumin	Potassium
Hemoglobin	Alkaline phosphatase	Sodium
Mean corpuscular hemoglobin	Alanine aminotransferase	Thyroid-stimulating hormone
Mean corpuscular hemoglobin concentration	Aspartate aminotransferase	Thyroxine free
Mean corpuscular volume	Bicarbonate	Total bilirubin
Platelet count	Blood urea nitrogen	Triiodothyronine free
Red blood cell count	C-reactive protein	Total cholesterol
White blood cell count with differential ^a	Calcium	Total protein
TBNK ^a	Chloride	Triglycerides
Coagulation		Creatinine
Prothrombin time	Creatine kinase	Uric acid
Activated partial thromboplastin time	Direct bilirubin	
International normalized ratio	Glucose	
URINALYSIS		
Appearance	Nitrite	
Bilirubin	Occult blood	
Color	pH	
Glucose	Protein	
Ketones	Specific gravity	
Microscopic examination of sediment	Urobilinogen	
BIOMARKERS		
Lymphocytes ^{a,b}		
hs-CRP ^b		
Fecal calprotectin ^b		
Immunophenotyping		
Proteomics		
STOOL SAMPLE^c		
Ova and parasites, C. difficile		

^a Total WBC, neutrophil, lymphocyte, and TBNK will be available for review prior to randomization. After randomization, the total WBC, neutrophil, lymphocyte, and CD4 T cell counts will be reviewed by an unblinded Medical Monitor who will provide instructions to the site Investigator in the event of significant lymphopenia. Investigators will remain blinded to the results after randomization. Refer to Section 9.8.4 for additional details.

^b Investigators will remain blinded to the results after randomization.

^c Stool sample for bacterial culture, ova, and parasite evaluation, and *C. difficile* assay at any point in the study when a participant becomes symptomatic, including worsening or return of disease activity.

β-hCG, beta-human chorionic gonadotropin; HBcAb, hepatitis B core antibody; HBsAb, hepatitis B surface antibody; HBsAg, hepatitis B surface antigen; HBV, hepatitis B virus; HCV, hepatitis C virus; HIV, human immunodeficiency virus; hs-CRP, high-sensitivity C-reactive protein; IgG, immunoglobulin G; RIBA, recombinant immunoblot assay; TBNK; T lymphocytes, B lymphocytes, natural killer lymphocytes; WBC, white blood cell

9.9.7.1. Screening

9.9.7.1.1. Drugs of Abuse

A standard urine drug screen will be performed ([Table 5](#)). Participants who test positive will be assessed for eligibility for study participation by the Investigator.

9.9.7.1.2. Pregnancy Testing

A serum pregnancy test for β -hCG will be performed on women of childbearing potential to determine eligibility. Post-screening urine pregnancy tests (β -hCG) should be performed as indicated in the Schedule of Assessments ([Table 6](#)). If at any point there is a case of a positive urine β -hCG test, the participant will have study treatment interrupted and a serum sample submitted to the central laboratory for β -hCG testing. If the serum test confirms positive, the participant will be withdrawn from the study treatment and all the necessary follow-up assessments will be conducted as per Section [9.9.9](#). If the serum test is negative, the participant may resume study treatment.

Negative pregnancy test results must be documented for all women of childbearing potential prior to dosing at applicable study visits. Women who are surgically sterile or who are postmenopausal are not considered to be of childbearing potential. Postmenopausal is defined as 12 consecutive months with no menses without an alternative medical cause.

9.9.7.1.3. Virology

Screening HIV antibody, hepatitis B (ie, HBsAg, HBcAb, HBsAb, and HBV DNA), and HCV (recombinant immunoblot assay, if positive HCV RNA should be used to confirm infection).

9.9.7.1.4. Clinical Chemistry, Hematology, Coagulation, and Urinalysis

Clinical chemistry, hematology, coagulation, and urinalysis parameters that will be assessed during the study are identified in [Table 5](#).

Participants will be in a seated or supine position during blood collection. All laboratory samples should be collected prior to the administration of study treatment at applicable visits (refer to Section [9.7](#) for timing of blood draws for PK).

9.9.8. Adverse Events

9.9.8.1. Definitions

9.9.8.1.1. Adverse Event

An adverse event is any untoward medical occurrence in a participant or clinical investigational participant administered a medicinal product and which does not necessarily have a causal relationship with this treatment. An adverse event can therefore be any unfavorable and unintended sign, symptom, or disease temporally associated with the use of a medicinal product, whether or not considered related to the medicinal product.

Adverse events can be any of the following:

- Unfavorable changes in general condition
- Subjective or objective signs/symptoms
- Concomitant disease or accidents
- Clinically relevant adverse changes in laboratory parameters over the course of the study

- Preexisting conditions that worsen in severity, increase in frequency, or have new signs/symptoms

9.9.8.1.2. Serious Adverse Event

An adverse event should be classified as an SAE if it meets one of the following criteria:

Fatal:	Adverse event resulted in death.
Life-threatening:	The adverse event placed the participant at immediate risk of death. This classification does not apply to an adverse event that hypothetically might cause death if it were more severe.
Hospitalization:	The adverse event required or prolonged an existing inpatient hospitalization. Hospitalizations for elective medical or surgical procedures or treatments planned before the signing of informed consent in the study or routine check-ups are not SAEs by this definition.
Disabling/ incapacitating:	The adverse event resulted in a persistent or significant incapacity or substantial disruption of the participant's ability to conduct normal life functions.
Congenital anomaly or birth defect:	An adverse outcome in a child or fetus of a participant exposed to the molecule or study treatment regimen before conception or during pregnancy.
Medically significant:	The adverse event did not meet any of the above criteria but could have jeopardized the participant and might have required medical or surgical intervention to prevent one of the outcomes listed above or involves suspected transmission via a medicinal product of an infectious agent.

9.9.8.1.3. Adverse Drug Reaction

An adverse drug reaction (ADR) in the pre-approval clinical experience with a new medicinal product or its new usages, particularly as the therapeutic dose(s) may not be established, is any noxious and unintended response to a medicinal product related to any dose. The phrase “responses to a medicinal product” means that a causal relationship between a medicinal product and an adverse event is at least a reasonable possibility (ie, the relationship cannot be ruled out).

9.9.8.1.4. Adverse Events of Special Interest

Based on the mechanism of action of etrasimod and prior experience with other agents acting via a similar mechanism, potential adverse events of special interest may be identified. In addition to appropriate reporting of these events as an adverse event or SAE, supplementary detailed information may be collected.

If there are any signs of PML-related symptoms, the Investigator should withhold study treatment and perform appropriate diagnostic evaluation per local standard of care at the first signs suggestive of PML. Typical symptoms associated with PML are diverse, progress over days to weeks, and may include progressive weakness on one side of the body or clumsiness of limbs, disturbance of vision, and changes in thinking, memory, and orientation leading to confusion and personality changes. The Investigator must notify the Medical Monitor of such an event.

Guidance for the Assessment of Potential Progressive Multifocal Leukoencephalopathy is provided in [Appendix 5](#).

9.9.8.1.5. Severity

The severity of each adverse event will be assessed at the onset by a nurse/or physician. When recording the outcome of the adverse event the maximum severity of the adverse event experienced will also be recorded. The severity of each adverse event will be graded according to the Common Terminology Criteria for Adverse Events, version 5.0 (CTCAE v5.0):

Grade 1:	Mild; asymptomatic or mild symptoms; clinical or diagnostic observations only; intervention not indicated.
Grade 2:	Moderate; minimal, local or noninvasive intervention indicated; limiting age-appropriate instrumental activities of daily living (ADL).
Grade 3:	Severe or medically significant but not immediately life-threatening; hospitalization or prolongation of hospitalization indicated; disabling, limiting self-care ADL (eg, preparing meals, shopping for groceries or clothes, using the telephone, managing money)
Grade 4:	Life-threatening consequences, urgent intervention indicated.
Grade 5:	Death related to adverse event

9.9.8.1.6. Relationship

The Investigator (or designee) will make a determination of the causal relationship of the adverse event to the study drug using a 4-category system according to the following guidelines:

Not Related: (Unrelated = flag no on the AEM Report form)	The adverse event is definitely caused by the participant's clinical state or the study procedure/conditions.
Unlikely Related: (Unrelated = flag no on the AEM Report form)	The temporal association between the adverse event and the drug is such that the drug is not likely to have any reasonable association with the adverse event.
Probably Related: (Related = flag yes on the AEM Report form)	The adverse event follows a reasonable temporal sequence from administration of the drug and cannot be reasonably explained by the known characteristics of the participant's clinical state, environmental, or toxic factors, or other modes of therapy administered to the participant.
Related: (Related = flag yes on the AEM Report form)	The adverse event follows a reasonable temporal sequence from administration of the drug, abates upon discontinuation of the drug, follows a known or hypothesized cause-effect relationship, and (if appropriate) reappears when the drug is reintroduced.

The Investigator will use clinical judgment to determine the relationship. Alternative causes, such as underlying disease(s), concomitant therapy, and other risk factors, as well as the temporal relationship of the event to the study treatment administration should be considered and investigated. The Investigator should consult the IB and the Product Information of marketed products within the drug class, when applicable. For each adverse event/SAE, the Investigator must document in the medical

notes that he/she has reviewed the adverse event/SAE and has provided an assessment of causality. There may be situations in which an SAE has occurred and the Investigator has minimal information to include in the initial report to the Sponsor; however, it is very important that the Investigator always make an initial assessment of causality for every event before the initial transmission of the SAE to the Sponsor. The Investigator may change his/her opinion of causality based on subsequent receipt of information and send an SAE follow-up report with the updated causality assessment. The causality assessment is one of the criteria used when determining regulatory reporting requirements.

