9.9.8.3.1. Serious Adverse Events

Any adverse event considered serious by the Investigator or that meets serious criteria must be reported to Pfizer Safety on the CT SAE Report Form upon awareness **and under no circumstances should the time to report exceed 24 hours of becoming aware of the event.**

If additional information is required or becomes available for a previously reported SAE, entry into CRF of the new or updated information should be completed and reported to Pfizer Safety on a new CT SAE Report Form **within 24 hours of awareness.**

Elective hospitalization and/or surgery for clearly preexisting conditions (eg, a surgery that has been scheduled prior to the participant's entry into the study) will not be reported as an SAE.

Any SAE that is ongoing when the participant completes the study or discontinues the study will be followed by the Investigator until the event resolved, stabilized, or returned to baseline status.

The Sponsor (via the In-Country Caretaker for Clinical Trial [ICCC]) is responsible for notifying the relevant regulatory authorities of any adverse event assessed by the Reporter (Investigator) or the Sponsor as:

- a) Serious, unexpected, and related, or
- b) Serious, expected, related and life-threatening or fatal

In addition, the ICCC is responsible for notifying the Investigator(s) of active sites, the head(s) of the active study sites, and, if applicable, the IRBs of all SAEs occurring during the study that are assessed by the Reporter (Investigator) or the Sponsor as related and unexpected.

The Investigator is responsible for notifying the head of the study site of SAEs and significant safety findings that occur at his or her site. The Investigator is also responsible for responding to requests for additional information made by the Sponsor, the head of the study site, or the IRB.

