#### 18.1.1.2. RELATIONSHIP TO STUDY TREATMENT

Relationship is classified as "not related", "unlikely related", "probably related", or "related" by the Investigator.

All related TEAEs will be summarized by SOC and PT. A "related TEAE" for the purpose of this summary is defined as a TEAE with relationship to study treatment of "probably related" or "related".

All TEAEs will be summarized by SOC, PT, and highest relationship (as reported on the eCRF, not grouped), with SOC and PT presented by descending frequency of etrasimod total group. If a subject reports a TEAE more than once within a SOC/PT, the AE with the worst-case relationship to study treatment will be used in this summary.

TEAEs with a missing relationship to study treatment will be regarded as "Related" to study treatment for summary tabulation purpose only.

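### The causality scale sets a stricter bar for a related event than the protocol's own definition of an adverse drug reaction, and leaves one kind of event without a category

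*Protocol*

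**What the plan says.** Protocol 9.9.8.1.6 has the investigator judge causality "using a 4-category system according to the following guidelines". Two categories carry the unrelated flag and two the related flag.

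- *Not Related* (flag no): "The adverse event is definitely caused by the" participant's clinical state or the study procedures.
- *Unlikely Related* (flag no): "The temporal association between the adverse event and the drug is such that the drug is not likely to have any reasonable association".
- *Probably Related* (flag yes): the event "follows a reasonable temporal sequence from administration of the drug and cannot be reasonably explained by the known characteristics of the" participant's clinical state, or by environmental or toxic factors or other therapy.
- *Related* (flag yes): plausible timing, and the event "abates upon discontinuation of the drug, follows a known or hypothesized cause-effect relationship, and (if appropriate) reappears when the drug is reintroduced".

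There is no *Possibly Related* category.

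Protocol 9.9.8.1.3 defines an adverse drug reaction. The link it requires is that "a causal relationship between a medicinal product and an adverse event is at least a reasonable possibility (ie, the relationship cannot be ruled out".

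The flag is then used in two places. In Protocol 9.9.8.3.1, the first criterion for notifying authorities is "Serious, unexpected, and related, or"; the second covers expected related events that are fatal or life-threatening. In SAP 18.1.1.2, a related TEAE is "defined as a TEAE with relationship to study treatment of 'probably related' or 'related". SAP 18.1.6 carries that definition, with missing relationship added, into its related rows: any related TEAE, related serious, related leading to discontinuation, related leading to interruption, and related by maximum severity.

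**The concern.** The protocol holds two standards for the same judgement. Under 9.9.8.1.3 an event counts as a drug reaction unless the link can be excluded. Under 9.9.8.1.6 it reaches the related flag only if nothing else reasonably explains it, or if stopping the drug gave supporting evidence.

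The case between the two is an ordinary one here. Every participant enters with active ulcerative colitis (Protocol 4.1), and oral 5-ASA and corticosteroids may continue (Protocol 6.7.2.1). An infection or a transaminase rise with compatible timing can therefore have a second possible explanation.

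At stake are the summaries that readers use to judge which events investigators attributed to etrasimod. The results are intended to support approval in Japan (Protocol 1.3).

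**Working it through.** No arithmetic tests this point; it rests on setting the definitions side by side. Take one event: timing compatible with the drug, another cause possible but not established, and no informative dechallenge (the drug was not stopped, or stopping it told nothing).

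| Standard | What it requires | Does the event meet it? | Flag |
|---|---|---|---|
| *Not Related* (9.9.8.1.6) | A definite other cause | No, the other cause is only possible | No |
| *Unlikely Related* (9.9.8.1.6) | Timing that argues against the drug | No, the timing is compatible | No |
| *Probably Related* (9.9.8.1.6) | Compatible timing and no other reasonable explanation | No, another explanation exists | Yes |
| *Related* (9.9.8.1.6) | Compatible timing, abatement off drug, known or hypothesized mechanism | No, there is no dechallenge evidence | Yes |
| Adverse drug reaction (9.9.8.1.3) | A link that cannot be excluded | Yes | n/a |

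So the event meets the adverse drug reaction definition and has no place on the scale.

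Next, follow the event if the investigator settles on *Unlikely Related*:

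1. The flag is no, so it fails the SAP 18.1.1.2 definition and is absent from the related rows in 18.1.1.2 and 18.1.6.
2. The SAP rule that counts a missing relationship as related does not help, because the field is filled in.
3. It remains among all TEAEs (SAP 18.1.1), TEAEs leading to discontinuation (18.1.2), serious TEAEs (18.1.3) and events of special interest (18.1.5) wherever it otherwise qualifies, because none of these filters on causality. A transaminase rise also appears in the threshold tables of 18.3.1.
4. It appears in the SAP 18.1.1.2 table by highest relationship, which keeps the four categories separate. There it is mixed with events whose timing really does argue against the drug, and the two kinds cannot be told apart.

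As a unit of scale only: at the planned 32 per group, one participant moved between flags shifts that group's related-event rate by 1/32 = 3.1 percentage points. The SAP says the actual number will be smaller, so one participant will count for more. This does not say how many participants are affected.

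**The case against.** The strongest reply is that little depends on the flag. Much of that stands.

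- **Expedited reporting.** A reader might infer that these events drop out of expedited reports. The documents do not support that. Under Protocol 9.9.8.3.1 every serious event reaches the Sponsor within 24 hours whatever its causality, and either the investigator's or the Sponsor's assessment can trigger notification. Section 9.9.8.3.2 ties expedited reporting to the adverse drug reaction concept itself. Potential Hy's law cases are serious events before their cause is settled (Protocol 16.6). A report is lost only if the Sponsor also judges the event unrelated. One residual gap is that, after the reporting period, 9.9.8.2.2 requires reports only of serious events suspected to be related, so the investigator's view comes first.
- **The *Related* category.** It has no condition about other causes, so an event with an alternative explanation can still be *Related* if it abates off drug and fits a mechanism. That narrows the gap to events without such evidence. It does not close it. In the Phase 2 study cited in Protocol 3.2, TEAEs led to stopping treatment in 5.8%, 8.0% and 0% of the 1 mg, 2 mg and placebo groups, against any-TEAE rates of 59.6%, 56.0% and 50.0%. That is 5.8/59.6 = 9.7%, 8.0/56.0 = 14.3% and 0% of participants with a TEAE. Temporary interruptions are not given, so this is context only.
- **Clinical judgement.** Section 9.9.8.1.6 calls the definitions guidelines and leaves room for judgement, so coding as *Unlikely Related* is an inference and not a certainty. But judgement must still end in one of four boxes, and the instruction to weigh alternative causes points away from *Probably Related*.
- **Effect on conclusions.** Assessment is double-blind, SAP 18 plans no between-group comparison of safety data unless otherwise specified, and no efficacy result uses the flag. All of this is correct.

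**Conclusion.** The scale in Protocol 9.9.8.1.6 contradicts the definition in 9.9.8.1.3. Followed as written, it can flag as unrelated an event that the protocol itself defines as an adverse drug reaction. The consequence is confined mainly to the related rows of SAP 18.1.1.2 and 18.1.6; the event stays in the safety data and in the tables that ignore causality.

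No size can be given. A reader might take the Phase 2 figures in Protocol 3.2 as a sign of undercounting: related against any TEAE is 7.7/59.6 = 12.9%, 10.0/56.0 = 17.9% and 5.6/50.0 = 11.2% for 1 mg, 2 mg and placebo. They do not show it. The documents do not give that study's causality scale, and low ratios are just as compatible with few drug-related events. Nor do the documents say what share of participants will have a competing explanation, since background therapy is permitted but no proportion is stated.

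The conclusion rests on a literal reading of the category definitions and on the assumption that at least some investigators would choose *Unlikely Related* when no category fits.

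**What to change.** In Protocol 9.9.8.1.6, bring the related flag into line with 9.9.8.1.3. Either add a *Possibly Related* category, flagged yes, for events with plausible timing that could also have another explanation, or remove the no-other-explanation condition from *Probably Related*. Make the same change to the related-TEAE definition in SAP 18.1.1.2 and to the footnote in 18.1.6.

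The study is being stopped early, so much of the data may already be coded on the present scale, and a changed scale alone would leave two scales in one small dataset. For recorded events, do one of the following:

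- Before unblinding, re-review every TEAE coded *Unlikely Related*, not only the serious ones, against 9.9.8.1.3.
- Add a supplementary SAP row that counts every TEAE other than *Not Related* as related. Beside the planned row, this shows how far the related-event rate depends on the gap, provided uncovered events were not coded *Not Related*.

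The cost is a wording change in the protocol and case report form guidance, plus a short blinded review or one extra table row. The drawback is a somewhat higher and less specific related-event rate.
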